While emotion regulation has been established as a primary component of child psychotherapy, biobehavioural domains have not been systematically integrated into treatment models. Studies have shown that treatment for adult disorders results in decreased emotion dysregulation, yet very few studies evaluate emotion regulation as a mechanism of change at the biobehavioural level¹⁶. To our knowledge, there have been no studies to date, examining emotion regulation as a mechanism of change in child and adolescent psychotherapy.

The primary objective of this study is to test biobehavioural regulation of negative emotion as a transdiagnostic mechanism of change in child psychotherapy. We hypothesize that psychotherapy will

improve emotion regulation of negative emotion in children, as compared to waitlisted controls. Additionally, we hypothesize that these anticipated changes in emotion regulation will be observed in biobehavioural markers, such as heart rate variance and performance on cognitive tasks.

The study will use an evidence-based transdiagnostic psychotherapy and machine learning models to characterize treatment response variations based on biobehavioural regulation. Within this objective, we have three specific aims of this study.

- 1) The first aim is to test biobehavioural regulation as a transdiagnostic mechanism of treatment response in psychotherapy for children with anxiety, depression and/or disruptive behaviour. Treatment response will be evaluated as pre-to-post change in diagnosis, symptoms, and the rate of symptom change. Biobehavioural regulation will be measured using a multimodal approach comprising validated parent- and child-report questionnaires, performance on behavioural and cognitive regulation tasks, and physiological reactivity.
- 2) The second aim is to apply association rule mining, a machine learning technique, to uncover patterns governing variations in the regulation components throughout the course of treatment. Patterns will be expressed in the form of data-driven and rule-based algorithms reflecting the relation between emotion regulation and treatment response.
- 3) The third aim is to engage our knowledge translation partners and stakeholders to incorporate the algorithms into a broader clinical decision-making framework and develop methods to pilot this framework in practice, to improve treatment response.
- 4) Finally, other research questions may focus on moderators of treatment course and treatment response.

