Measures of symptoms, such as the Child Behaviour Checklist, list items that may be indicative of imminent risk, such as suicide ideation. If high scores are reported on these items, research staff will flag it and discuss the next steps with the principal investigator. If appropriate, the research staff and principal investigator will contact the participant, provide them with additional resources, and direct them to emergency services.

Overview of Measurement Model

Primary Construct	Measurement	Reporter P = Parent; C = Child; R = Researcher	Pre/Post	Weekly/Quarterly
Child Diagnosis and Symptoms				
Impairment	Brief Impairment Scale	P	x	

	(modified)			
Symptoms	Child Behavior Checklist (CBCL)	P	x	Quarterly
	Youth Self-Report (YSR)	C (11 – 15)	x	Quarterly
	Top Problems Assessment (TPA)	P, C, R	x	Quarterly
	Behavior and Feelings Survey (BFS)	P, C	x	Weekly
Trauma	Child and Adolescent Trauma Screener (CATS)	P, C	Pre-only	
Child Biobehavioural Regulation of Negative Emotion				
Questionnaires	Child and Adolescent Dispositions Scale – Negative Emotionality (CADS)	P, C	x	Weekly
	Positive and Negative Affect Scale (PANAS)	C	x	Quarterly
Physiology	Heart Rate Variability (HRV)	C	x	Quarterly
	Skin Conductance Level (SCL)	C	x	Quarterly
Behavioural/ Cognitive Tasks	Modified Trier Social Stress Test for Children (TSST-C)	C, R	x	Quarterly
	Piñata Task	C, R	x	Quarterly
	Cognitive Reappraisal Task (CRT)	C, R	x	Quarterly
	Observational Coding of Parent-Child Interaction	P, C, R	x	Quarterly
Parent Functioning, Family Functioning, and Parenting				
Parent Functioning	Brief Symptom Inventory (BSI-18)	P	x	
	Parenting Stress Index-Short Form (PSI-SF)	P	x	
	Difficulties in Emotion Regulation Scale Short Form (DERS-SF)	P	x	
Family Functioning	Family Functioning Style Scale (FFSS)	P	x	
	Confusion, Hubbub, and Order Scale (CHAOS)	P	Pre-only	
Parenting	Coping with Children's Negative Emotions Scale (CCNES)	P	x	
Covariates				
Demographics	Demographics	P	Pre-only	

	Questionnaire			
Puberty	Tanner Stages Assessment	P, C	Pre-only	
Medication	Medication Questionnaire	P	x	Quarterly
Additional Services	Service Access Form	P	x	

Impairment

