*TPA*²²: The Top Problems Assessment (TPA) is a brief, idiographic procedure that aims to identify the most important problems from the perspective of the child and their parent(s)/caregiver(s). The assessment will be conducted at pre- and post-test, quarterly during the intervention/waitlist period, and at follow up. At each assessment, the parent(s)/caregiver(s) and child will be asked to identify one to three primary issues that they would like to work on in treatment and will rate the severity of each problem.

*BFS*²³: The Behavior and Feelings Survey (BFS) is a 12-item scale with parallel versions for the child and the parent. The items assess internalizing problems, externalizing problems, and total problems. It takes less than 5 minutes to complete and will be completed by the child and parent(s)/caregiver(s) each week over the course of the intervention/waitlist period.

*CATS*²⁴: The *Child and Adolescent Trauma Screener (CATS)* is a brief screener of traumatic events and symptoms of PTSD. It consists of possible traumatic events (e.g. natural disaster, physical abuse), and if one or more are reported to be present, it screens for symptoms of traumatic stress (e.g. hyperarousal, nightmares). It has been validated for children aged 7 – 17, and will be completed by parent(s)/caregiver(s) at pre-test, post-test, and at follow up.

Biobehavioural Regulation of Negative Emotion Questionnaire

*CADS*²⁵: The *Child and Adolescent Dispositions Scale (CADS)* is a valid and reliable measure that was developed to assess the developmental propensity of conduct disorder. The negative emotionality subscale consists of 7 items and is reported by the child. The original CADS scale refers to the child as he/she. For the purposes of this study, we created a modified version of the CADS with gender-neutral language. Children who score highly on negative emotionality items are more likely to be easily upset by frustrations and setbacks, to which they respond to with intense anger. It will be completed weekly by parent(s)/caregiver(s), and by children who are 9 years or older.

*PANAS*²⁶: The *Positive and Negative Affect Scale (PANAS)* is a valid and reliable measure that is intended to assess an individual's moods. It consists of 20 single-word items that are a positive (e.g. excited) or negative (e.g. scared) affect. The PANAS will be complete by children at the pre-test, post-test, quarterly, and follow up assessments.

Behavioural/Cognitive Tasks

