Preliminary analyses will test for significant differences in demographic factors between the MATCH and waitlist groups; significant factors will be covaried in our models. In the unlikely event that medication discrepancies are discovered between the two treatment groups, we will equate the groups by imposing propensity scores-based weighting in the analysis. An exploratory factor analysis (EFA) will examine whether the emotion regulation variables load onto a broad latent construct. Variables that do not load on the same factor will be examined independently within our mediation models. Latent Growth Curve (LGC) mediation modeling, which will account for the nested structure of the data as well as potentially unequally spaced time points, will test whether improvements in emotion regulation mediate improvements in symptoms as a result of MATCH treatment. We will conduct two types of mediation analyses corresponding to our operationalization of treatment response – pre-post change and trajectory of change. First, emotion regulation (latent biobehavioural regulation factor(s) from the EFA) will be modeled as a latent change from baseline to the 3-month quarterly assessment, and symptom change (CBCL/YSR internalizing and externalizing scores) will be modeled as a latent change from baseline to the post assessment. Our predictor will be specified as MATCH vs. Waitlist to ensure we can derive conclusions about the impact of MATCH on emotion regulation and symptoms. To test the mediated effect, we will apply the recommended bootstrap-based product of coefficients, which will yield bias-corrected 95% CIs based on the recommended asymmetric CI method. Second, to understand trajectories of change during MATCH treatment, we will apply LGC modeling to examine latent slopes of change in emotion regulation (weekly CADS) and symptoms (weekly BFS) and explore the temporal relations between the two trajectories. This will allow us to understand the temporal order and bi-directionality of changes in regulation and symptoms. In both modeling approaches, we will co-vary child age, gender/sex, medication use, puberty status, ethnicity, and treatment fidelity. We will apply an intent-to-treat approach and full information maximum likelihood estimation to account for potential bias caused by missing data.

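### Top Problems are named afresh at each visit and the baseline problems are not re-rated, so pre-to-post TPA severity can compare different problems and is likely to understate improvement

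*Protocol*

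**What the plan says.** The TPA entry under Symptoms sets the timing: "The assessment will be conducted at pre- and post-test, quarterly during the intervention/waitlist period, and at follow up". It then gives the procedure: "At each assessment, the parent(s)/caregiver(s) and child will be asked to identify one to three primary issues that they would like to work on". The same sentence goes on to have them score how severe every problem so named is. Naming and rating are thus one step, repeated at every visit. No part of the protocol says that problems named at the pre-treatment visit are kept and rated again, or how severity is scored when the list or its length changes.

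The table in Overview of Measurement Model places the TPA under symptoms, at pre/post and quarterly, with parent, child and researcher as reporters. The first aim in Rationale and Study Objectives says: "Treatment response will be evaluated as pre-to-post change in diagnosis, symptoms, and the rate of symptom change".

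Data Analysis is narrower. For the pre-post model, "symptom change (CBCL/YSR internalizing and externalizing scores) will be modeled as a latent change from baseline to the post assessment". The trajectory model takes its symptom slopes from the weekly BFS. The TPA appears in neither model, and Sample Size does not mention it.

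**The concern.** A change score needs the same target at both times. Here the family names what it wants to work on now. A problem that has resolved is likely to leave the list, and whatever matters most at that point takes its place. The improvement in the first problem is then recorded nowhere.

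The number of problems may also move between one and three. If a family stops naming its milder problems and nothing else changes, the mean rating goes up and the sum goes down.

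The loss would fall mainly on the arm that improves, which pulls an arm comparison of TPA severity towards no difference. A later analysis plan cannot repair this, because ratings of the baseline problems that were not taken at the post visit do not exist.

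**Working it through.** The protocol gives no effect size, SD or score definition for the TPA, so there is no stated figure to reproduce. The check has two parts: what follows from the wording, and how large the effect could be under stated assumptions.

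**Direction.** Suppose families name their currently most severe problems.
- At the post visit, the mean of the three most severe problems cannot be below the mean of the three baseline problems. The within-child fall under fresh naming is therefore equal to or smaller than the fall under re-rating.
- For the arm comparison, let treatment lower each baseline problem by 0.5 SD and every other problem by no more than that. The mean of the top three then falls by at most 0.5 SD, so fresh naming cannot overstate the effect in this setting.

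**Size.** All inputs are assumptions:
- K candidate problems per child (3, 5, 8 or 12), with baseline severities X independent and standard normal.
- Severity at post without treatment: Y = rX + √(1 − r²)·E, where E is standard normal and r (0.4, 0.6 or 0.8) is the retest correlation.
- B is the set of the three largest X. Treatment lowers problems in B by 0.5 SD and all others by 0.5s SD, with s = 0, 0.5 or 1.
- Re-rated effect: mean Y over B, control minus treated. This is 0.50 SD by construction.
- Fresh effect: mean of the three largest Y, control minus treated.

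Arm difference in SD under fresh naming (200,000 simulated children; range over r from 0.4 to 0.8):

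| K | s = 0 | s = 0.5 | s = 1 |
|---|---|---|---|
| 3 | 0.50 | 0.50 | 0.50 |
| 5 | 0.33 to 0.38 | 0.42 to 0.45 | 0.50 |
| 8 | 0.23 to 0.32 | 0.37 to 0.42 | 0.50 |
| 12 | 0.17 to 0.28 | 0.35 to 0.40 | 0.50 |

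As shares of the true 0.50 SD, the s = 0 range for K of 5 to 12 is 0.17/0.50 = 34% to 0.38/0.50 = 76%. For s = 0.5 it is 0.35/0.50 = 70% to 0.45/0.50 = 90%.

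**A caution on within-arm change.** Re-rated scores regress to the mean. In a similar simulation with r of 0.5 or 0.8 and 5 to 12 problems, the baseline top three fell by 0.11 to 0.59 SD in untreated children. So not all of the within-arm gap between the two methods is lost improvement. The arm difference is free of this, because it affects both arms alike.

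**The case against.** Four points can be made on the other side.

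1. *The TPA carries no specified analysis.* Data Analysis ties its two mediation analyses to the trial's two operational forms of treatment response, and these use the CBCL/YSR and the weekly BFS. This stands. A reader who joins the first aim to the measurement table might infer that the trial's main treatment-response result is biased. The protocol does not support that: no TPA change analysis is specified, and the sample size does not rest on the TPA.

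2. *Loss is not inevitable.* A reader might infer that fresh naming shrinks any real improvement. It does not. A problem that is named again shows its lower rating, and the arm difference is intact if all problems improve equally or the child has only three. MATCH Treatment describes a transdiagnostic therapy adapted to comorbid problems, so some benefit beyond the first-named problems is plausible. The column s = 0 is the least favourable branch, not the expected one.

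3. *The selection rule is assumed.* Families name what they want to work on, which need not be what is most severe. This stands, and it makes both direction and size less certain. The two scores still need not refer to the same problems.

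4. *The entry summarises an instrument whose manual is cited but not at hand, and fresh naming does serve the stated purpose of finding the most important problems.* The form in use may already carry baseline problems forward. The protocol's wording does not say so, however. It expressly places the naming step at each assessment, which is more than a silence to be filled elsewhere.

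**Conclusion.** The point holds for the TPA as a supplementary repeated symptom measure. As written, pre-to-post TPA severity can compare different problems and different numbers of problems, and it is likely to understate improvement.

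The size is not derivable from the protocol. With a true 0.5 SD effect on the three baseline problems, families naming their most severe problems, 5 to 12 candidate problems and retest correlations of 0.4 to 0.8, fresh naming shows about 0.17 to 0.38 SD with no benefit to other problems and 0.35 to 0.45 SD with half the benefit. It shows 0.50 SD, no loss, if all problems improve equally or there are only three.

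The mediation models and the sample size are not affected. The change is still worth making, since it is cheap now and the missing ratings cannot be recovered later.

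**What to change.** Amend the TPA entry under Symptoms so that the one to three problems named at the pre-treatment visit are re-rated by the same informant at every quarterly, post and follow-up visit. Problems newly named at later visits go on a separate list outside the change score, so the picture of current concerns is kept. Any TPA change should be read as a difference between arms, because re-rated scores also fall in untreated children through regression to the mean.

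If baseline problems are already re-rated in practice, one added sentence settles the matter. Otherwise, flag data collected under the current wording. Pairs in which the same problem happens to recur can be identified, but they are a selected subset.

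The cost is a revised form and assessor script, and at most three additional ratings per informant per later visit.

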Videos will be recorded using an ipadaudio will be recorded via a digital recorder for the purpose of transcription, qualitative coding and fidelity checks. Recordings will be transferred via secure file transfer to the research team at the University of Guelph for transcription and coding. Once transferred, the video and audio recordings on the devices will be deleted from the recording devices and will be stored on encrypted hard drives at CAMH and secure servers at Guelph. The folder containing all video/audio recordings will be accessible only to members of the research team who have received appropriate training. Video and audio recording files will be retained at both sites for 10 years.

Once a participant agrees to participate in this study and signs the consent form, a research note will be generated on their medical record.

Participant Randomization

Stratified randomization by gender (boy, girl and non-binary) and age group (ages 8 – 10, 11 – 13, 14 – 15) will be employed to ensure balance in sample size between treatment and control groups with regard to gender and age randomization. REDCap will be employed and will allocate the participants based on a computer-generated randomization list using random block sizes. Allocation concealment will be achieved since the person making this assignment will have no awareness or control over the randomization schedule.

Data Collection

Measurement for this study will be multi-modal and will consist of questionnaires for the parent(s)/caregiver(s) and child, behavioural/cognitive tasks, a parent-child interaction task, and physiological measures. Data collection will be conducted by trained research staff with the supervision of the study investigators. The study investigators will conduct regular meetings with the

Parent and child questionnaires will be administered electronically via REDCap. In order to ensure consistency between the two sites (CAMH and Guelph), we will use a shared REDCap Project to administer questionnaires to participants. REDCap questionnaires, behavioural/cognitive tasks, parent-child interaction task, and physiological measures will be completed at each study visit. Additionally, parents and children will complete brief weekly questionnaires via secure, encrypted links from REDCap.

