CCNES³⁹: The Coping with Children's Negative Emotions Scale is a self-report assessment which presents parent(s)/caregiver(s) with hypothetical scenarios in which their child is upset or angry (e.g. My child falls off their bike and breaks it, then gets upset and cries). Each scenario provides 6 possible responses to the child's distress and the parent(s)/caregiver(s) are asked to rate their likelihood of utilizing that response. Each response represents a different way of responding to a child's distress. It will be completed by the parent(s)/caregiver(s) of the child at pre- and post-test, and follow up.

Covariates

Prior to treatment, demographic information (e.g. child's age, sex, gender identity, ethnicity, language) will be provided by the child's parent(s)/caregiver(s). Demographic information is important for data analysis purposes and will allow us to identify any different patterns of treatment responses in different groups (e.g. treatment response in male children compared to treatment response in female children). Parents will report on their country of birth and their child's country of birth, as parents and children born outside of Canada often face immigration difficulties, cultural adjustment issues, and language barriers. Additionally, this allows us to evaluate the representativeness of our sample compared to the Canadian population. Information will be collected from the participants' health record on the number of sessions attended, and will be included as a control variable.

The parent(s)/caregiver(s) and child will report on the child's pubertal development, as indicated by the Tanner Stages Assessment⁴⁰. Information on pubertal development is needed because puberty can influence the physiological measures of emotion regulation being used in this study (e.g., heart rate variability). Parent(s)/caregiver(s) will report on their child's medication status pre- and post-test, at follow up, and quarterly during the course of treatment. To assess for satisfaction with treatment, parent(s)/caregiver(s) will complete the Youth Services Satisfaction Survey for Families⁴¹⁰.

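### Demographic covariates outside the fixed list enter the mediation models only if they differ significantly between randomised arms, so chance rather than prognosis selects them; the numerical effect is probably small

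*Protocol*

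**What the plan says.** Three adjustment rules stand in one paragraph of the protocol's Data Analysis section.

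- **Test-based rule for demographics:** "Preliminary analyses will test for significant differences in demographic factors between the MATCH and waitlist groups; significant factors will be covaried in our models".
- **Conditional rule for medication:** "In the unlikely event that medication discrepancies are discovered between the two treatment groups, we will equate the groups by imposing propensity scores-based weighting".
- **Unconditional list:** "In both modeling approaches, we will co-vary child age, gender/sex, medication use, puberty status, ethnicity, and treatment fidelity".

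The paragraph does not say how the three fit together, which demographics are tested, or at what level.

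The Covariates section gives age, sex, gender identity, ethnicity and language as examples of the demographics collected, and adds: "Parents will report on their country of birth and their child's country of birth". Under Participant Randomization, allocation is computer-generated and concealed, with "Stratified randomization by gender (boy, girl and non-binary) and age group". Symptoms and emotion regulation are modelled as latent change from baseline.

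**The concern.** With concealed randomisation, the null hypothesis of a baseline test is true by design, and a significant result is a chance imbalance. Precision depends on how strongly a covariate predicts the outcome, and the test carries no information on that. The rule therefore admits a useless factor that happened to differ and leaves out a prognostic one that happened to balance. For age group and gender the test is emptier still, since both are stratification factors.

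Two things are at stake. Part of the covariate set in the main mediation analysis cannot be known until data by arm have been examined. And some of the precision that a fixed list would secure may be given up.

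The medication rule raises a related question. It makes weighting depend on an observed difference between arms, in a variable that both models already adjust for.

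**Working it through.** **Inputs from the protocol.** N = 168, d = 0.5 and α = 0.05 (Sample Size); the fixed list (Data Analysis); the demographics named (Covariates).

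**Assumptions.** 1:1 allocation, two-sided 5% tests, three to five factors tested, and the added R² of those factors. The protocol gives none of these.

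**The plan's own figure.** The protocol gives no number for the covariate rule. Its N = 168 comes from a mediation simulation. With a total effect of 0.5 and 25% mediated, the indirect effect is 0.5 × 0.25 = 0.125. Splitting this as a = 0.5 and b = 0.25 gives a simulated power of 0.80 at N = 168, which agrees. Other splits (a from 0.3 to 0.6) give 0.49 to 0.80. So 168 is a reasonable size for the check below, though the match depends on the split.

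**Step 1: what the test decides.** Age, gender/sex and ethnicity are in the models whatever the test shows. Of the demographics named, that leaves essentially three: language, the child's country of birth and the parents' country of birth. The questionnaire may hold others.

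**Step 2: chance of entry.** For k independent tests at 5%, P(at least one enters) = 1 − 0.95^k.

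- k = 3: 1 − 0.857 = 14%
- k = 5: 1 − 0.774 = 23%

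Each single factor enters with probability 5%, whether it is strongly prognostic or not at all.

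**Step 3: precision at stake.** Fixed adjustment multiplies the residual standard deviation by √(1 − R²), where R² is the part added by these factors. At R² = 0.05 this is √0.95 = 0.975, a fall in standard error of at most about 2.5%.

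**Step 4: power.** A linear model for the arm effect was simulated (N = 168, d = 0.5, 6,000 trials per row):

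| Added R² | Factors | Test-selected | Fixed | Difference (points) |
|---|---|---|---|---|
| 0.01 (r = 0.10) | 1 | 89.2% | 89.6% | 0.4 |
| 0.02 (r = 0.15) | 1 | 90.2% | 90.6% | 0.4 |
| 0.05 (r = 0.22) | 1 | 89.8% | 90.9% | 1.1 |
| 0.05 (r = 0.10 each) | 5 | 89.3% | 90.3% | 1.0 |
| 0.20 (r = 0.20 each) | 5 | 90.3% | 94.4% | 4.1 |
| 0.25 (r = 0.50) | 1 | 91.0% | 96.2% | 5.2 |

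**Step 5: error rate under the null.** The simulation error of a 5% rate is √(0.05 × 0.95 / 6000) = 0.3 points. With five factors and R² = 0.05, rejection is 5.1% (test-selected) against 5.0% (fixed), so there is no difference. At R² = 0.20 it is 4.3% against 4.8%. Where a distortion appears, it is conservative. A factor stays out only in trials where its imbalance is small, so the estimate then varies less than the unadjusted standard error implies.

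**Limit of the check.** It concerns the arm effect in a linear model. The protocol judges the mediated effect by a bootstrap interval for a product of coefficients, so the figures indicate order of magnitude only.

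**The case against.** The strongest reply is that the paragraph already does most of what good practice asks. Five patient characteristics are adjusted for unconditionally, two of them (age and gender) are also strata, and the outcome is modelled as change from baseline. What is left to the test is a few demographics with probably modest extra prognostic value. Naming further covariates is often left to the analysis plan, which is not shown. This stands as far as size is concerned. It does not rescue the rule: the protocol does not leave the choice open but states a method for making it, and that method is unsound.

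Four stronger readings are tempting, and the documents do not support them.

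- **That the covariates as a whole are picked by significance tests.** The unconditional list rules this out.
- **That power falls by 4 to 5 points or more.** This needs an added R² of 0.20 to 0.25 from factors not otherwise in the model. Nothing in the protocol suggests that language or country of birth adds so much beyond the fixed covariates.
- **That a chance covariate enters in 40% of trials.** This needs ten tested factors (1 − 0.95^10 = 0.40), and the protocol gives no such count.
- **That the medication weighting merely responds to chance imbalance.** This is true only of a difference at baseline. Medication is also recorded at quarterly and post visits, and the text does not confine the discrepancies to baseline. A difference that arises during treatment or waiting need not be chance.

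**Conclusion.** The point holds in a narrow form. The protocol states a rule that lets chance imbalance decide which of the remaining demographics enter the mediation models, and so makes part of the model depend on arm data. At 5% per test, the chance that at least one enters is 14% for three factors and 23% for five; both counts and the test level are assumptions. The cost in precision is probably small: about 1 power point or less if the added R² is at most 0.05, also an assumption. A reader might infer inflated false positives, but the check shows none, and any distortion of standard errors is conservative. The reason to act is that the rule is unsound and easily removed, not that it threatens the trial's conclusions.

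On medication, the supported finding is an unexplained overlap: a fixed covariate and a data-triggered weighting for the same variable, with no threshold and no time point for the trigger.

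**What to change.** 1. Delete the rule that tests demographic factors between arms and adjusts for the significant ones.
2. Name one baseline covariate list in advance, chosen on prognostic grounds: the baseline factors already listed (age, gender/sex, pre-test medication use, puberty status, ethnicity) plus any other demographic judged prognostic. Treatment fidelity is not a baseline factor, so it does not belong in this list.
3. Report baseline balance descriptively by arm, without significance tests.
4. Reconcile the medication weighting with the fixed medication covariate. Weighting should not be triggered by a baseline difference. If it is meant for medication changes after randomisation, say so and make it a sensitivity analysis.

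This is a change of wording, best made before any data are examined by arm. It needs no new data and leaves fewer analyses to run.
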